#### 24.4 Analysis Populations

Safety Population. All patients who receive at least 1 dose of 1 agent in the investigational treatment regimen (i.e. either GX-188E or P) will be included in the analysis of safety, regardless of the duration of treatment.

DLT-evaluable. Unless doses are missed within the first two weeks of treatment (i.e., Week 1 Day -1 to Week 2 Day 7) due to DLT(s), a patient must receive all of the planned administrations of both agents (GX-188E and P) within the DLT-evaluation period to be considered evaluable for DLT. If a patient misses any treatment within the first two weeks of the study for reasons other than a DLT, the patient will be considered non-evaluable for DLT and replaced.

Efficacy Evaluable Population. All patients who discontinue the study treatment regimen early due to treatment-related toxicity will be considered evaluable for efficacy. Patients who discontinue study due to disease-related death, unequivocal tumor progression or with at least 1 post-baseline tumor assessment must have received at least 45 days of treatment to be considered evaluable for efficacy. Patients in Part B and C who do not meet the aforementioned requirements will be considered non-evaluable for response and may be replaced. Patients from Part A, who receive the recommended Phase 2 regimen and who meet the aforementioned criteria for the Efficacy Evaluable Population will be included in the analysis for Part B and C. The following table provides further, more specific details.

Table 7. Determination of Patients to be Included in Efficacy Evaluable.

Patient Cohort	Reason for Discontinuation	Number of Days on Protocol Treatment	Include in Efficacy Evaluable Population (Yes/No)?
Part A receiving RP2 regimen*	Protocol-Defined Dose Limiting Toxicity (DLT), or other toxicity	Not applicable	Yes, included in Efficacy Evaluable Population
Part A receiving RP2 regimen*	Disease-related death, unequivocal tumor progression or at least 1 post-baseline tumor assessment	< 45 days	No
Part A receiving RP2 regimen*	Disease-related death, unequivocal tumor progression or at least 1 post-baseline tumor assessment	≥ 45 days	Yes, included in Efficacy Evaluable Population
Part A, receiving dose > RP2 regimen*	Any	Not applicable	No
Part B and C	Disease-related death, unequivocal tumor progression, or at least 1 post-baseline tumor assessment	< 45 days	No, patient may be replaced
Part B and C	Disease-related death, unequivocal tumor progression, or at least 1 post-baseline tumor assessment	≥ 45 days	Yes, included in Efficacy Evaluable Population
Part B and C	Toxicity	Not applicable	Yes, included in Efficacy Evaluable Population

\*RP2 regimen = Recommended Phase 2 regimen of GX-188E

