## STATISTICAL METHODS

Maximum 60 patients are planned for enrollment into this clinical trial.

Safety Analysis. All patients who receive at least one dose of the investigational treatment will be included in the safety population. All safety analyses will be performed on the safety population. Adverse Events (AE) will be coded according to the MedDRA adverse event dictionary. The results will be tabulated to examine their frequency, organ systems affected, and relationship to study treatment. The results of laboratory tests will be evaluated similarly.

Efficacy Analysis. Efficacy results, including but not limited to ORR24, BORR, DOR, DCR, TTR, PFS, and OS for patients enrolled into Part A will be provided using descriptive statistics. Objective responses will be evaluated according to both RECIST v1.1 and Response Evaluation Criteria In Solid Tumors for Immunotherapeutics (iRECIST).

Note: Confirmatory scans are required for all determinations of objective response (PR or CR), Stable disease(SD) and disease progression (PD). Confirmatory scans must be performed at least 4 weeks later.

Part B follows a Simon Two-Stage mini-max design. The sample size for the first stage of Part B is 15 patients; the sample size for the second stage is 13 patients, for a total of 28 patients. Patients from Part A without a DLT, who receive the recommended Phase 2 treatment regimen and who are considered evaluable for efficacy will be included in the analysis for Part B Stage 1. For a null hypothesis ORR24 of 0.15 and an alternative hypothesis ORR24 of 0.35, the sample size of 28 subjects will provide a one-sided significance level of 5% and a power of 80%. For Stage 1, a minimum of three patients must demonstrate a response (PR or better) to proceed to the second stage. Study has passed the first stage of Simon-Two stage design. If Stages 1 and 2 are completed, a minimum of 8 patients must demonstrate a response (PR or better) to reject the null hypothesis. If a patient's responses could not be confirmed, that patient will not be included in the primary efficacy population for ORR24.

Part C is to evaluate efficacy in larger patient population.

In Keynote-158 study (pembrolizumab monotherapy in patients who have progressed with standard of care systemic therapy), ORR in total patients (i.e. regardless of PD-L1 status) and with CPS  $\geq 1$  were 12.2% and 14.6%, respectively.

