#### 10.5 Number of Patients

Maximum 60 patients are planned for recruitment to both Parts A, B and C of this study. As previously described in Section 10.2 above, minimum of 6 patients will be enrolled into Part A. The maximum number of safety evaluable patients to be enrolled into Part A is 18.

Part B of this study employs a Simon-Two Stage Design. A minimum of 15 efficacy evaluable patients (see Section 24.4), which may include some patients from Part A, will be included in the analysis for Stage 1. If 3 or more patients in Stage 1 experience objective responses (i.e., Partial Response or better), the study will move into Part B Stage 2 and an additional 13 patients

will be treated, for a total of 28 efficacy evaluable patients. Study has passed the first stage of Simon-Two stage design.

If at least 8 of the 28 subjects enrolled in Part B, experience an objective response who are considered evaluable for efficacy, it will be considered that ORR satisfies the criteria for study expansion and additional 17 subjects (at least) will be enrolled in Part C to evaluate efficacy further in larger population (N=45~60). Refer to the Section 24.3 Sample Size and Power for detailed assumptions for sample size estimation.

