# 22.1.2 **Tumor Imaging During the Study**

The first on-study imaging assessment should be performed approximately 9 weeks ( $\pm 3$  days]) from the date of treatment initation. Subsequent tumor imaging should be performed every 9 weeks ( $\pm 3$  days at Week 19,  $\pm 7$  days for subsequent timepoints) or more frequently if clinically indicated. Imaging timing should follow calendar days and should not be adjusted for delays

in cycle starts. Imaging should continue to be performed until disease progression is identified by the investigator (unless the investigator elects to continue treatment and follow iRECIST), the start of new anticancer treatment, withdrawal of consent, or death, whichever occurs first. All supplemental imaging must be submitted to the central imaging vendor.

Objective response and stable disease should be confirmed by a repeat imaging assessment. Tumor imaging to confirm SD, PR or CR should be performed at least 4 weeks after the first indication of a response is observed. Participants will then return to regular scheduled imaging, starting with the next scheduled imaging time point. Participants who receive additional imaging for confirmation do not need to undergo the next scheduled tumor imaging if it is less than 4 weeks later; tumor imaging may resume at the subsequent scheduled imaging time point. Note: Response does not typically need to be verified in real time by the central imaging vendor.

Per iRECIST (Appendix 6 and Section 22.3), disease progression should be confirmed by the site 4 to 8 weeks after site-assessed first radiologic evidence of PD in clinically stable participants. Participants, who have unconfirmed disease progression may continue on treatment at the discretion of the investigator until progression is confirmed by the site, provided they have met the conditions detailed in Section 22.3. Participants who receive confirmatory imaging do not need to undergo the next scheduled tumor imaging if it is less than 4 weeks later; tumor imaging may resume at the subsequent scheduled imaging time point, if clinically stable. Participants, who have confirmed disease progression by iRECIST, as assessed by the site, will discontinue study treatment. Exceptions are detailed in Section 22.3.

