#### 5.4. EFFICACY EVALUABLE POPULATION

All patients who complete the study will be included into the efficacy evaluable population. These patients will be identified by using the "Subject's status?" with answer "Completed trial" from end of study page of CRF.

All patients who discontinue the study treatment regimen early due to treatment-related toxicity will be considered evaluable for efficacy. These patients will be identified as those with DLT. Patients who discontinue study due to disease-related death, unequivocal tumor progression or with at least 1 post-baseline tumor assessment must have received at least 45 days on protocol treatment to be considered evaluable for efficacy. Patients who discontinue study due to disease-related death will be identified by using the "Primary reason for premature discontinuation from study" with answer "Death" from end of study page of CRF and the "Was death disease related" with answer "Yes" from death details page of CRF. Patients who discontinue study due to unequivocal tumor progression will be identified by using "Primary reason for premature discontinuation from study" with answer "Disease Relapse or Progression" from end of study page of CRF. Patients who discontinue study with at least 1 post-baseline tumor assessment will be identified as those with at least one RECIST/iRECIST Overall Response data on RECIST/iRECIST Overall Response page of CRF after screening visit. Patients in Part B and Part C who do not meet the aforementioned requirements will be considered non-evaluable for response and may be replaced. Patients from Part A, who receive the recommended Phase 2 regimen and who meet the aforementioned criteria for the Efficacy Evaluable Population will be included in the analysis for Part B and Part C. The following table provides further, more specific details.

Document: \\ieedc-vnac01\Biosdata\Genexine\GX-188E\GYA02599\Biostatistics\Documentation\SAP

Author: [name] Version Number: 1.1

Version Date: 05Sep2022

Template No: CS\_TP\_BS016 Revision 6 Reference: CS\_WI\_BS005

Analysis Plan Page 16 of 48

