#### Table 1. Determination of Patients to be Included in Efficacy Evaluable Population

Patient Cohort	Reason for Discontinuation	Number of Days on Protocol Treatment	Include in Efficacy Evaluable Population (Yes/No)?
Part A receiving RP2 regimen*	Protocol-Defined DLT, or other toxicity^	Not applicable	Yes, included in Efficacy Evaluable Population
Part A receiving RP2 regimen*	Disease-related death, unequivocal tumor progression or at least 1 post- baseline tumor assessment	< 45 days	No
Part A receiving RP2 regimen*	Disease-related death, unequivocal tumor progression or at least 1 post- baseline tumor assessment	≥ 45 days	Yes, included in Efficacy Evaluable Population
Part A, receiving dose > RP2 regimen*	Any	Not applicable	No
Part B and Part C	Disease-related death, unequivocal tumor progression, or at least 1 post-baseline tumor assessment	< 45 days	No, patient may be replaced
Part B and Part C	Disease-related death, unequivocal tumor progression, or at least 1 post-baseline tumor assessment	≥ 45 days	Yes, included in Efficacy Evaluable Population
Part B and Part C	Toxicity ^	Not applicable	Yes, included in Efficacy Evaluable Population

\*RP2 regimen = Recommended Phase 2 regimen of GX-188E

 $Document: \underline{\label{locality} Nocumentation} Biosdata \underline{\label{locality} GX-188E\underline{\label{locality} GYA02599\underline{\label{locality} Biosdata}} \\$ 

Author: [name] Version Number: 1.1

Version Date: 05Sep2022

Template No: CS\_TP\_BS016 Revision 6 Reference: CS\_WI\_BS005

Effective Date: 02Dec2019

^ Toxicity = Any dose limiting toxicity (DLT).

Analysis Plan Page 17 of 48

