#### **15.1.** PRIMARY EFFICACY ENDPOINTS

The primary efficacy variable is BICR-assessed ORR24 by RECIST 1.1 in Part B and C.

Best overall response within 24 weeks (BOR24) is the best objective response achieved within the first 24 weeks of treatment prior to study discontinuation. All available response designations will contribute to the BOR24 determination. If a patient's BOR24 could not be confirmed, that patient will not be included in the primary efficacy population for ORR24. Additional patients will be enrolled to meet the study hypothesis. Any CR or PR must be confirmed by a sequential assessment that is at least 4 weeks apart. The confirmation rule is defined in Table 2 (please refer to RECIST 1.1 [1]). The confirmed response will be determined before analysis. The number and percentage of patients in each category of best overall response CR, PR, SD, PD or Not Evaluable (NE) will be provided.

ORR24 is the proportion of efficacy evaluable patients who achieve an objective response (PR or CR) within 24 weeks prior to study discontinuation. The number and percentage of patients who achieve best overall response of PR or CR will be summarized.

If the first responses can be confirmed by the second response within 24 weeks of treatment. they will be included as responses for ORR24. Also, If the first response within 24 weeks is confirmed by the second response after 24 weeks of treatment, the first response should be included as response for ORR24.

Table 2. Best overall response when confirmation of CR and PR is required per RECIST 1.1 Guideline

Overall response  First time point	Overall response Subsequent time point	Best overall response
CR	CR	CR
CR	PR	PR, or SD provided at least 28 days' duration, otherwise PD a
CR	SD	SD provided at least 28 days' duration, otherwise PD

Document: \(\)\ieedc-vnac01\\Biosdata\\Genexine\\GX-188E\\GYA02599\\Biostatistics\\Documentation\\SAP\)

Author: [name] Version Number: 1.1

Version Date: 05Sep2022

Template No: CS TP BS016 Revision 6 Reference: CS WI BS005

Analysis Plan Page 29 of 48

CR	PD	SD provided at least 28 days' duration, otherwise PD
CR	NE	SD provided at least 28 days' duration, otherwise NE
PR	CR	PR
PR	PR	PR
PR	SD	SD
PR	PD	SD provided at least 28 days' duration, Otherwise PD
PR	NE	SD provided at least 28 days' duration, Otherwise NE
NE	NE	NE

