#### OS

Overall survival is defined as the time from treatment initiation until death from any cause. Median OS time (months) is the timepoint at which the probability of survival equals 50% in the efficacy evaluable population. Patients developing no event will be censored on the last known survival date. Patients providing no follow-up information will be censored on the day of first dosing. Kaplan-Meier method will be used to estimate median OS and the corresponding 95% CI. Kaplan-Meier curves will be constructed to provide a visual presentation of the OS rate change with time.

6-month OS rate is the proportion of efficacy evaluable patients who are alive 6 months after treatment initiation. The OS rate and 95% CI at 6 months will also be summarized.

OS will be displayed for Part A, Part B and Part C.

Waterfall, Spider, Swim-lane and forest Plots

A waterfall plot will be prepared to visually present the best percentage change from baseline in sum of diameters in target lesions for each patient grouped by PD-L1 status, HPV type, and histologic type.

A Spider Plot will be used to visualize changes in sum of diameters in target lesions with best overall response by BICR according to RECIST 1.1. With a Spider Plot, post-baseline measurements are compared to the baseline. Thus, the data plotted is the percent change from baseline over the period of patient evaluation. Each leg of the "spider" represents a unique patient.

Swim-lane Plot for Tumor Response will be presented to show tumor assessment by at each

Document: \\ieedc-vnac01\Biosdata\Genexine\GX-188E\GYA02599\Biostatistics\Documentation\SAP

Author: [name] Version Number: 1.1

Version Date: 05Sep2022

Template No: CS\_TP\_BS016 Revision 6 Reference: CS\_WI\_BS005

PROTOCOL GX-188E-005

Analysis Plan Page 34 of 48

visit. Specifically, the Swim-lane plot will show total time to tumor response, whether the response was complete or partial, when the response started/ended and censoring information of the patient grouped by PD-L1 status, HPV type, and Histologic type.

These plots will be displayed only for Part C.

In Part C, a forest plot will be used to display BICR Assessed BORR according to RECIST v1.1 across subgroups.

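### The 45-day rule takes early disease-related deaths and progressions out of the primary efficacy set, so ORR24, PFS and OS read too high; the likely effect on the Part C decision is limited

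*Protocol*

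**What the plan says.** Protocol 24.4 sets a minimum exposure for patients who leave the study early. Those who go because of "disease-related death, unequivocal tumor progression or with at least 1 post-baseline tumor assessment must have received at least 45 days of treatment" if they are to enter the Efficacy Evaluable Population. SAP 5.4 has the same rule: they "must have received at least 45 days on protocol treatment to be considered evaluable for efficacy". Protocol Table 7 and SAP Table 1 apply it by cohort. For Parts B and C with fewer than 45 days, the entry is "No, patient may be replaced"; for Part A it is a plain no.

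Patients who stop for treatment-related toxicity are included whatever their time on treatment. The SAP narrows this group to those with a DLT.

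This set carries the efficacy results. In SAP 15.1, ORR24 "is the proportion of efficacy evaluable patients who achieve an objective response (PR or CR) within 24 weeks prior to study discontinuation", and the Part C success rule acts on that proportion. Median OS is "the timepoint at which the probability of survival equals 50% in the efficacy evaluable population", and median PFS is defined in the same set.

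Two provisions soften this. SAP section 15 plans ORR24, BORR and DCR in the safety population as sensitivity analyses. Protocol 24.5 allows, but does not require, a description of responses in non-evaluable patients.

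**The concern.** Membership of the primary set is decided after treatment starts, by an outcome that is itself treatment failure. A patient who dies of the disease or clearly progresses before day 45 could hardly have been counted as a responder. In Protocol 22.1.2, "The first on-study imaging assessment should be performed approximately 9 weeks" from the start of treatment, which is after day 45, and SAP 15.1 requires a CR or PR to be confirmed at least 4 weeks later. Removing such patients shrinks the denominator and leaves the numerator as it was.

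The primary estimate is therefore too high by a factor that the plan does not state. PFS and OS run from treatment initiation, so removing early events raises those curves too. A close primary result could be decided by who was excluded.

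**Working it through.** **Inputs from the documents.** Part C: null 12.2%, alternative 37%, two-sided 0.05, 97% power, 25% dropout, N = 60; success if the Clopper-Pearson lower 95% limit exceeds 12.2% (Protocol 24.3). Part B: at least 3 of 15, then at least 8 of 28, null 15%, alternative 35%; with 7 or fewer responders Part C does not open (Protocol 10.4). Ceiling: "Maximum 60 patients are planned for enrollment into this clinical trial" (synopsis), repeated in Protocol 10.5.

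**Assumptions.** e, the share of treated patients removed by the rule, is not in the documents; a range is shown. Excluded patients are taken as non-responders.

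**1. The plan's own figures.** With n = 45 the exact rule needs at least 11 responders (lower limit 12.9%) and has 97.4% power at 37%; 45/(1 − 0.25) = 60. The Simon design has error 4.6% at 15% and power 80.3% at 35%. Both match the protocol.

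**2. Bias in the estimate.** Expected evaluable ORR24 = p/(1−e). For p = 37%:
- e = 5%: 0.37/0.95 = 38.9%
- e = 10%: 0.37/0.90 = 41.1%

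**3. Part C false success.** Let n = 60(1−e) be the evaluable number and x the smallest count whose lower limit exceeds 12.2%. The probability is that of at least 3/15, then at least 8/28, then at least x/n, carrying patients forward. With the rule the response probability is 0.122/(1−e), which assumes that 12.2% is an all-treated rate. The last column uses 0.122.

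| e | n | x | with the rule | same n and x, no inflation |
|---|---|---|---|---|
| 5% | 57 | 13 | 0.8% | 0.5% |
| 10% | 54 | 13 | 1.0% | 0.4% |
| 15% | 51 | 12 | 2.0% | 0.6% |
| 20% | 48 | 12 | 2.5% | 0.5% |
| 25% | 45 | 11 | 4.6% | 0.7% |

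The nominal 2.5% upper tail is passed only above about e = 20%; at n = 47 (e = 21.7%) the figure is 3.9%.

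**4. Part B.** The Simon error at 0.15/(1−e) is 6.0% at e = 5% and 7.8% at e = 10%, if 15% is an all-treated rate. The protocol labels Part B exploratory.

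**5. Boundary case.** 13/59 = 22.0%, lower limit 12.3%: success. 13/60 = 21.7%, lower limit 12.1%: failure. Here one exclusion reverses the conclusion.

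**6. PFS and OS.** Every early death removed is an OS event removed, so OS is biased upward. For PFS, SAP Table 3 has two rows that can both fit a death before any scan: death before two consecutive missed assessments is an event at the date of death, while no evaluable post-baseline assessment is censored at first dose. Under the second row, putting such a patient back leaves the Kaplan-Meier curve unchanged.

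**The case against.** The strongest reply is that the practical damage is small and partly covered already.

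- **An all-treated ORR24 is planned.** A reader might infer that the inflated rate is the only one reported. SAP section 15 says otherwise: early failures are in the safety-population denominator. This stands. What remains is that the safety-population result does not govern success and does not extend to PFS or OS.
- **e may be small.** Entry requires ECOG 0–1 and life expectancy of at least 6 months. Radiologic progression before day 45 needs an unscheduled scan, and Protocol 22.3 discourages stopping clinically stable patients before progression is confirmed. This also stands. The plan's only figure for losses, 25% dropout, covers all causes and is not e.
- **Part C error is largely protected.** Ignoring the Part B gates, the upper tail at e = 25% and n = 45 would be 10.3%, and a reader might infer serious inflation from that. The gates bind, so the table above is the relevant one. Figures for 60 evaluable patients after replacement would also break the ceiling in Protocol 10.5: "Maximum 60 patients are planned for recruitment to both Parts A, B and C of this study".
- **The boundary case is selected.** At an evaluable rate of 37%, the chance that the evaluable set passes while 60 treated fails is 0.6% with 59 evaluable, 0.9% with 57 and 1.6% with 54.
- **The 12.2% benchmark.** The protocol describes it as the rate in total patients regardless of PD-L1 status, which does not settle which patients were in its denominator. The error figures rest on that assumption; the 1/(1−e) bias in the estimate does not.

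**Conclusion.** The concern holds in a limited form. The primary set excludes early treatment failures, and the direction of bias in ORR24 is upward: by 1/(1−e) if those excluded are non-responders, with e unknown and possibly small. The effect on the Part C conclusion is limited. False success stays within 2.5% up to about e = 20%, given the Part B gates, at most 60 treated and 12.2% as an all-treated rate. A result on the boundary can still turn.

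OS is biased upward. PFS is too, but a reader might infer that the 6-month PFS rate carries the same 1/(1−e) factor. SAP Table 3 does not support that, because the amount depends on whether a death or progression without a post-baseline scan is an event or is censored at first dose.

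A reader might also infer that the rule catches patients who progress at the Week 10 scan, since first and last doses on Day 1 of Weeks 1 and 7 span 6 × 7 + 1 = 43 days. The documents do not define how days on treatment are counted for this rule, so that cannot be asserted.

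The point should be fixed before database lock: the direction is clear, the size is uncertain, and the remedy needs no new data.

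**What to change.** - In Protocol Table 7 and SAP Table 1, delete the exclusion and replacement below 45 days for disease-related death and unequivocal progression, and count these patients as non-responders in the primary ORR24. The simplest form is to make all patients treated at the recommended Phase 2 regimen the primary denominator and keep the Efficacy Evaluable set as supportive.
- Report OS and PFS on the all-treated set, and state in SAP Table 3 that a death before any post-baseline scan is a PFS event. Without that statement, changing the set does not by itself repair PFS.
- Amend before database lock. Leave Part B decisions already taken as made, and report Part B on both sets.

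**Cost.** A mid-trial amendment in an open-label study, a less favourable ORR24, and lower power. If 37% is the evaluable rate, all-treated power is P(X ≥ 14) with n = 60 and p = 0.37(1−e): 98.3%, 96.5%, 88.8% and 81.7% at e = 5%, 10%, 20% and 25%. The evaluable-set test has 99.3%, 98.5%, 97.2% and 97.4% at the same e, and the plan states 97%. If 37% is itself the all-treated rate, power at 60 is 99.2%.

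Two neighbouring matters need their own reconciliation: how patients with unconfirmed responses are handled, and whether 60 means patients treated or patients evaluable.
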